10.0 ADVERSE EVENT REPORTING

Participants will be interviewed at each visit and prompted to discuss any adverse events; such events will be recorded. In the event of a serious adverse event, the IRB will be notified per posted requirements and in full compliance with federal guidelines for research in human subjects. An event, whether study-related or not, will be assessed based on description of the event/pathology, onset, duration, severity, analgesics or other medication taken, and possible causality.

11.0 CRITERIA FOR SUCCESS

11.1 Grafts

The success criteria for this investigation are determined as follows: Grafts will be deemed successful if there are no reported symptoms or clinical signs of post-application allergy, toxic reactions or evidence of gross local or systemic infections.

Histological and histomorphometric analyses will provide evidence of the relative success or failure of graft materials to enhance formation of new osseous tissue in extraction sockets. Results will be compared and between experimental groups.

A site that fails to meet the stated criteria for success, or where the width of the ridge remains too narrow for implant insertion will be re-grafted (an offer that patients may decline). The site may receive an implant at a later date but the site will be exited from the study results.

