2.3 Hypotheses and Specific Aims

The trial will test two hypotheses:

Hypothesis-1: Grafting with Bone Allograft is an efficacious method of enhancing the development of new bone fill in extraction sockets.

Hypothesis-2: Bone Allograft/Amniotic allograft will aid osseous healing and will preserve alveolar ridge dimensions of extraction sockets more effectively than extraction sites grafted with Bone Allograft alone.

Specific Aims

- 1: Compare the efficacy of bone grafting with and without enrichment with amnion.
- 2: Compare alveolar ridge dimensions between groups after 7 weeks of post-extraction healing.
- 3: Compare soft tissue healing between groups at week-1, week-2, week-4 and after 7 weeks of post-extraction healing.

- 4: Assess quantitative bone fill between groups after 7 weeks of post-extraction healing
- 5: Compare qualitative bone fill between groups after 7 weeks of post-extraction healing.
- 6: Assess and compare the relationship of osseous healing and implant stability at insertion across groups after 8 weeks of post-extraction healing.
- 7: Compare implant stability between groups at 12 months and 24 months post-restoration.
- 8: Assess changes in longitudinal crestal bone level between groups at 12 and 24 months after permanent prosthetic attachment.

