4.9 Tissue Biopsy and Implant Placement

After reviewing the CBCT scans the investigator will determine whether or not the sockets have enough bone-fill to enable the surgical placement of implants. The diameter and length of the implants placed will be determined by the surgeon/investigator based on the tooth location, anatomy, and bone volume determined from the CT scan prior to placement. Immediately prior to implant placement, a tissue biopsy will be harvested from the center of one grafted site. Implants will be placed following standard procedures outlined in the Manual of Procedures.

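### Section 11.1 defines graft success by tolerability alone and removes both intolerant and too-narrow sites from the results, so a graft that fails to preserve the ridge never counts as a failure.

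*Combined protocol and SAP*

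**What the plan says.** Section 11.1 of the protocol has three parts.

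- **The success rule.** "Grafts will be deemed successful if there are no reported symptoms or clinical signs of post-application allergy, toxic reactions or evidence of gross local" (the sentence then adds systemic infection). It has no bone or ridge element.
- **Laboratory evidence.** "Histological and histomorphometric analyses will provide evidence of the relative success or failure of graft materials to enhance formation of new osseous tissue". No threshold is given, and this part does not alter the rule.
- **The exit rule.** It applies to "A site that fails to meet the stated criteria for success, or where the width of the ridge remains too narrow for implant insertion". Re-grafting is offered and may be declined. Then: "The site may receive an implant at a later date but the site will be exited from the study results".

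The aims lie elsewhere. Hypothesis-2 in Section 2.3 states that the amnion graft "will preserve alveolar ridge dimensions of extraction sockets more effectively than extraction sites grafted with Bone Allograft alone". Specific aim 2 is to "Compare alveolar ridge dimensions between groups after 7 weeks of post-extraction healing". Section 4.9 says that, after review of the CBCT scans, "the investigator will determine whether or not the sockets have enough bone-fill to enable the surgical placement of implants". Neither Section 4.9 nor Section 11.1 gives a width or fill criterion. The statistical analysis plan (Section 13.4) does not mention exited sites.

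**The concern.** The trial grafts sockets to preserve the ridge for an implant, yet the rule labelled success asks only whether the material was tolerated. The word 'or' in the exit rule confirms that ridge width lies outside the success criteria. The exit rule then removes the very sites where the graft did not achieve its purpose. These exclusions depend on an outcome that the graft is meant to change, so they may differ between arms.

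Two things are at stake. First, any graft success rate reported under Section 11.1 says nothing about the ridge and cannot fall below 100% among retained sites. Second, if exit also discards the week-7 CBCT data, the comparison of ridge dimensions is made only among sites that did well enough, which shrinks a real difference.

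**Working it through.** The plan states no effect size, event rate or power, so there is no figure of its own to reproduce. The check is a classification of sites under Section 11.1, followed by illustrations with assumed rates.

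**Step 1. Where each kind of site ends up**

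| Tolerability | Ridge | Meets success rule | In study results | Counted as |
|---|---|---|---|---|
| met | adequate | yes | yes | success |
| met | too narrow | yes | no | neither |
| not met | either | no | no | neither |

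Only the first row remains, so retained success is n/n = 100% in each arm whatever the graft does.

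**Step 2. Effect on the counts**

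Inputs: 10 participants per group (Section 3.1). Assumed: one site each, no tolerability failures, and f narrow ridges per arm. As written the rate is (10 − f)/(10 − f). Counting failures it is (10 − f)/10.

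| Narrow, control v test (assumed) | As written | Counted as failures | Fisher p, two-sided |
|---|---|---|---|
| 1 v 0 | 9/9 v 10/10 | 9/10 v 10/10 | 1.0 |
| 2 v 1 | 8/8 v 9/9 | 8/10 v 9/10 | 1.0 |
| 3 v 1 | 7/7 v 9/9 | 7/10 v 9/10 | 0.58 |
| 4 v 1 | 6/6 v 9/9 | 6/10 v 9/10 | 0.30 |
| 4 v 0 | 6/6 v 10/10 | 6/10 v 10/10 | 0.087 |

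For the two cases with four failures in all, P(k in control) = C(10,k)·C(10,4−k)/C(20,4), with C(20,4) = 4845.

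- 4 v 0: 2 × 210/4845 = 0.087.
- 3 v 1: 2 × (1200 + 210)/4845 = 0.58.

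**Step 3. Effect on ridge dimensions, if exit also drops the week-7 scan**

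Assume width is normal with SD 1, control mean 0 and test mean d, and that sites below a common cut-off c are removed. The retained mean is μ + φ(c − μ)/[1 − Φ(c − μ)].

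Worked case: d = 0.5 and 30% of control sites removed, so c = −0.524.

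- Control: 0.348/0.700 = 0.497.
- Test: 0.5 + 0.236/0.847 = 0.779.
- Retained difference: 0.28 SD.

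| True difference | 10% of control removed | 20% | 30% |
|---|---|---|---|
| 0.5 SD | 0.39 | 0.33 | 0.28 |
| 1.0 SD | 0.84 | 0.73 | 0.64 |

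**Step 4. Whether another measure catches the failure**

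- Histology: the core is taken just before the implant goes in (Section 4.9), within the drilling sequence (Section 6.3). No core is provided for where no implant is placed. Whether another site of the same participant may supply one is not stated.
- Implant survival runs from surgical placement (Section 13.3), and implant success (Section 11.3) presupposes an implant. Sites never implanted enter neither.
- CBCT: the week-7 scan (Section 4.8) precedes the implant decision, so it can show the failure. Whether the data survive exit is not stated.

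**The case against.** The strongest reply is that no planned analysis uses a graft success rate. It is absent from the synopsis outcomes, from the endpoints in Section 13.3 and from Section 13.4. The effect of interest is measured directly, by week-7 ridge dimensions (aim 2) and bone fill (aim 4) on a scan taken before anyone decides about an implant. On this view Section 11.1 sets a safety criterion beside separate efficacy evidence, and the label is a matter of taste.

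Part of this stands. Hypothesis-2 concerns ridge dimensions and does not depend on the binary label, so the rule does not contradict it. A reader might infer that the trial cannot detect a ridge effect at all. The documents do not support that, because the CBCT comparison is planned. But Section 11.1 presents its rule as the investigation's success criteria, and its exit sentence is unqualified, so the CBCT comparison is not clearly protected either.

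It is also fair that a redefined endpoint would seldom discriminate with 10 per arm: 3 v 1 gives p=0.58. The case for change therefore does not rest on power. Finally, blinding is stated only for laboratory technicians (Section 6.3), so the adequacy judgement may be open to influence. That limits the proposed endpoint but does not justify leaving failures out.

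**Conclusion.** The concern holds as one of definition plus outcome-dependent exclusion. Graft success is tolerability only, and both kinds of failure leave the results, so the retained rate is 100% in both arms. In the assumed cases, counting the narrow ridges moves the rates to between 9/10 v 10/10 and 6/10 v 10/10.

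A reader might infer that a too-narrow site is still reported as a success, giving 10/10 v 10/10 in the 4 v 0 example. The documents do not support this. Such a site meets the wording of the success rule, but the exit sentence removes it, so it counts as neither success nor failure and the figure is 6/6 v 10/10.

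The 100% follows from the text, provided that exit applies to every such site, including those where re-grafting is declined. The narrow-ridge counts are assumptions, as are one site per participant and the absence of tolerability failures. The shrinkage in Step 3 applies only if exit removes the week-7 data, and it treats the narrow-ridge decision as a fixed cut-off on the measured width.

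**What to change.** 1. In Section 11.1, rename the present rule *graft tolerability*.
2. Define *graft success* as tolerability met and the site judged adequate for implant placement at the planned visit without re-grafting. Use the investigator determination in Section 4.9 and record it on the CRF. Section 4.9 speaks of bone fill and Section 11.1 of ridge width, so state which the determination covers and how it is made.
3. Amend the exit sentence. Such sites count as graft failures and stay in the denominator of all randomised, grafted participants. Their week-7 CBCT data stay in the ridge-dimension and bone-fill comparisons. Later implant data may be censored.
4. Compare arms at participant level, since all of a participant's sites receive the same graft (Section 4.2). State a rule for participants with several sites, for example that any failed site makes the participant a failure.

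Clinical handling of re-grafting is unchanged. The cost is wording in Sections 11.1 and 13.4 and, if not already present, one CRF item. The investigator already makes the assessment, but the documents do not show that it is recorded. There are two downsides: the reported success rate will be less favourable, and the adequacy judgement is not stated to be blinded, which should be acknowledged when the result is reported.

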11.2 Implant Survival

At the 12 and 24-month follow-up evaluations, participants will be interviewed to determine if any pain or numbness has been experienced since implant placement or has developed since the previous interview. The implant sites will be examined for any evidence of implant failure including implant suppuration and erythema.

If signs or symptoms of implant failure are observed at any time during the course of the study, a periapical radiograph will be obtained and inspected for signs of radiolucency. The investigator will make assessment of implant status and if a failure is determined, will be reported on the appropriate CRF. At the investigator's discretion a medical and/or surgical attempt to rescue the implant may be made.

11.3 Implant Success

An implant will be considered successful as long as it remains immobile when tested with instrument pressure at follow-up evaluations and offers stable anchorage to a functional prosthetic attachment. A successful implant shows no evidence of fracture or signs of peri-implant radiolucency on an intraoral radiograph (using a paralleling technique strictly perpendicular to the implant bone-interface), or persistent or irreversible signs and/or symptoms of pain, infection, neuropathies or paresthesia.

12.0 COSTS TO PARTICIPANTS

12.1 Procedure Fees

No fees will be charged to participants for teeth extraction, socket grafting materials, the implant devices, implant surgery, CBCT scans, radiographs, photographs, bone biopsy analysis, or clinical evaluations for the entire study.

Participants will be expected to pay a **\$1,000 fee for each implant restored.** This one-time-only fee will cover costs related to laboratory fees and materials for the fabrication of the implant restoration prosthesis. This fee is to be billed to participants prior to the initiation of any surgical procedures.

Study visits are not designed to take the place of routine dental care. Over the course of the study, participants will be expected to continue with regular dental check-ups with a dentist of their choice. Should the need arise patients who do not have a regular dentist of record will be referred in the appropriate manner for any non-study related dental treatment. Costs for non-study related treatment will be charged to the participant's account or to their insurance provider in the usual manner per dental school policy and will not be paid for from the study account

12.2 Payment to Participants

Participants will be paid **\$50** after completing the 12-month visit and **\$50** after completing the final study visit at 24 months following implant insertion.

13.0 OUTCOMES AND ANALYSES

The study is structured to provide both subjective and objective data; study sites will be followed, data will be captured at placement and at 12 and 24 months after implants are placed.

13.1 Objective Data

Bone biopsies preserved in the trephines and stored in formalin will be submitted to UAB's CMBD Core Laboratory. Trephine core 2x6 mm will be stained with hematoxylin and eosin and processed for histologic and histomorphometric analysis. Amount of bone fill and remaining bone graft (% of new bone fill, % of residual graft and % of soft tissue) material will be determined and compared across groups. Torque measurements will be recorded for each site at implant placement.

Cone Beam Computed Technology (CBCT) will be used to capture quantitative natural bone fill and bone fill following grafting applications at each extraction site.

Image analysis software will be used to capture images from the standardized radiographs taken at 12 and 24 months following implant placement. Analysis procedures will assess the implant/bone interface and measure changes in adjacent crestal alveolar bone levels over time.

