4.6 Grafting Extraction Sockets

After extractions, sockets will be grafted according to each participant's assigned randomization group.

Group-1: Each socket will be grafted with Bone Allograft mixed with sterile saline.

4.6.1a Irrigate sockets with sterile saline.

4.6.1b Pack the graft into each of the study sites using mild pressure achieving complete fill of the sockets.

4.6.1c Trim a 3 mm section of collagen plug and secure it over the grafted areas with 5.0 Monocryl crossing mattress sutures.

Group-2: Each socket will be grafted with Amnion Graft mixed with Bone Allograft

4.6.2a Irrigate sockets with sterile saline.

4.6.2b Pack the graft into each of the study sites using mild pressure achieving complete fill of the sockets.

4.6.2c Trim a 3 mm section of collagen plug and secure it over the grafted areas with 5.0 or 6.0 Monocryl crossing mattress sutures.

After completion of procedures, the Essix retainer will be fitted and placed.

A baseline, post-grafting CBCT scan will be made to include images of each study site. Prescriptions for anti-bacterial mouth wash, antibiotics, and pain relief will be provided based on individual patient

needs. An ice-pack will be dispensed. Verbal and written home care instructions will be given and the patient will be scheduled for a follow-up appointment.

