5.0 CONE BEAM COMPUTED TOMOGRAPHY

Cone-Beam Computed Tomography (CBCT) will be used in this trial to obtain a 3-dimensional database of each participant's anatomy from the volumetric tomography. Axial, sagittal, and cross-images will be reconstructed to measure tooth socket volume. CBCT imaging is used in state-of-the-art dentistry to aid treatment planning of complex implant cases and is considered best practice in dental imaging. The CBCT produces a highly accurate scan of the head and neck. The image can then be visualized as a virtual reproduction of the jaw that is accurate to within a tenth of a millimeter (0.10mm). A CBCT scan allows the dental surgeon to view the anatomy in many different planes and

provides precise knowledge of the disposition of anatomical structures. These views enable the dental surgeon to select an implant with the most appropriate configurations to fit the anatomy of each individual patient.

Participants in this study will have 2 CBCT scans made; the first will aid in the initial treatment planning, the second scan will be used to assess bony healing of the grafted sites prior to implant placement. The images will be captured using I-Cat, Cone Beam CAT scanning equipment, manufactured by Imaging Sciences and designed especially for imaging the skull in the dental setting. CBCT scans are acquired through a series of rapid pulses in a single pass, exposing the patient to radiation for the equivalent of 3 seconds per image. These scans compare favorably to hospital-based CT scans of the head and neck area where exposure is 30 times greater.

A Cone Beam Computed Tomography (CBCT) scan will be made at baseline (immediately post-grafting), and at 7 weeks after the grafting.

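### CBCT 'bone fill' is read from sockets already packed with graft and is not defined to exclude it, so it should be reported as graft plus bone and new-bone claims left to the week-8 histomorphometry

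*Combined protocol and SAP*

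**What the plan says.** Section 4.6 gives the same packing instruction for both groups: "Pack the graft into each of the study sites using mild pressure achieving complete fill of the sockets". The scan comes afterwards: "A baseline, post-grafting CBCT scan will be made to include images of each study site". Section 5.0 fixes the two time points: "A Cone Beam Computed Tomography (CBCT) scan will be made at baseline (immediately post-grafting), and at 7 weeks after the grafting". The same section also says of the two scans that "the first will aid in the initial treatment planning", which is hard to square with a scan made after extraction and grafting.

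The only CBCT measurement described is in section 5.0: "Axial, sagittal, and cross-images will be reconstructed to measure tooth socket volume". No region, density threshold or rule for telling graft from new bone is given. Section 13.1 nevertheless states: "Cone Beam Computed Technology (CBCT) will be used to capture quantitative natural bone fill and bone fill following grafting applications at each extraction site".

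For the biopsy, section 13.1 does separate the tissues. Histomorphometry yields the percentages "of new bone fill, % of residual graft and % of soft tissue", compared across groups. Section 11.1 names histology and histomorphometry as the evidence on new osseous tissue.

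Aim 4 in section 2.3 reads: "Assess quantitative bone fill between groups after 7 weeks of post-extraction healing". Section 13.4 adds paired tests of change in bone growth from baseline, without naming the measurement.

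**The concern.** Within section 13.1 the term bone fill does two jobs. For the core it is a tissue distinguished from residual graft. For CBCT it is a reading of a socket that was filled with graft by design, with nothing said about removing the graft from the count. The phrase natural bone fill has no source at all, because every study site is grafted and no empty socket is scanned.

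The change from baseline has a related problem. The core is taken once, so it cannot supply a change. The CBCT pair is therefore one natural candidate for the bone growth tested in 13.4. The other is the radiographic bone height along the implant in 13.3. If the CBCT pair is used, growth is measured from a starting image that already shows whatever part of the graft is radiopaque.

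At stake is how Aim 4 and the osseous-healing part of Hypothesis-2 are read. A difference in leftover graft could be reported as a difference in bone healing. The plan does not say which measure decides if CBCT and histology disagree.

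**Working it through.** The plan gives no figure to reproduce: there is no expected fill, SD, effect size or power. The check is an identity with assumed tissue percentages, followed by the precision of the measure that does separate the tissues.

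**Inputs from the documents.** Sockets completely filled before the first scan (4.6); second scan at week 7 (5.0); one core per participant (6.3); 10 participants per group (3.1); two-sided tests at 0.05 (13.4).

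**Assumed.** N = % new bone and G = % residual graft at week 7. r = visibility of graft on CBCT, from 0 (not visible) to 1 (as visible as bone). The documents state none of these.

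**Step 1, between-arm difference at week 7.** Radiographic fill = N + r × G. Test minus control = ΔN + r × ΔG, so the error as a measure of new bone is r × ΔG.

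| Control N/G | Test N/G | True ΔN | ΔG | CBCT, r = 0 | r = 0.5 | r = 1 |
|---|---|---|---|---|---|---|
| 30/30 | 40/30 | +10 | 0 | +10 | +10 | +10 |
| 30/30 | 40/20 | +10 | −10 | +10 | +5 | 0 |
| 25/40 | 35/15 | +10 | −25 | +10 | −2.5 | −15 |
| 30/30 | 30/20 | 0 | −10 | 0 | −5 | −10 |
| 30/30 | 30/40 | 0 | +10 | 0 | +5 | +10 |

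Row 1 is unbiased at every r, and the r = 0 column is unbiased in every row. Row 2 masks a gain. Row 3 reverses it once r exceeds 10/25 = 0.4. Rows 4 and 5 produce a difference where there is none. Bias therefore needs both a visible graft and unequal residual graft.

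**Step 2, change from the post-graft scan within one arm.** Take the packed graft as 100% of the socket, so baseline fill = 100r. Change = N + r × G − 100r = N − r × (100 − G). For N = 30 and G = 30:
- r = 0: 30 − 0 = +30
- r = 0.5: 30 − 35 = −5
- r = 1: 30 − 70 = −40

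The same 30 points of new bone can appear as growth or as loss. If both arms start from the same baseline fill, the between-arm difference in change is again ΔN + r × ΔG.

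**Step 3, precision of histomorphometry.** With 10 cores per arm and 80% power, the normal approximation gives (1.960 + 0.842) × √(2/10) = 1.25 SD. The exact t calculation gives 1.32 SD. With 8 cores per arm (assumed) it is 1.51 SD. With 10 per arm, exact power is 0.56 for a 1.0 SD difference and 0.40 for 0.8 SD.

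**The case against.** The strongest reply is that the plan already assigns new bone to histology (11.1, 13.1) and compares residual graft as well. Aim 4 says neither new bone nor change from baseline, and a week-7 comparison between arms does not use the first scan. Both arms receive the same bone allograft (4.3), so the documents give no reason to expect unequal residual graft. Total fill also has a use of its own: section 4.9 uses the CBCT scans to judge whether an implant can be placed. All of this stands, and it rules out several stronger readings that a reader might infer:

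- *CBCT cannot answer Aim 4.* Not supported. A week-7 comparison of total radiographic fill fits the aim's wording.
- *CBCT never measures new bone.* Not supported. If the graft does not show on CBCT, week-7 fill tracks new bone. The documents do not say whether the allograft is mineralised, and the exclusion for hypersensitivity to DBM in Table 1 leaves a demineralised component possible.
- *Amnion is expected to speed graft turnover, so CBCT will mislead.* Not supported. Section 1.2 proposes faster bone formation and soft-tissue healing and does not mention allograft resorption.
- *CBCT should be confined to ridge dimensions.* Not supported. The core is taken just before implant placement (4.9), and sites that fail or stay too narrow leave the study results (11.1). Cores may therefore be missing where healing is worst, while week-7 CBCT is planned for every site.

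The reply does not remove the ambiguity. Sharing one allograft does not guarantee equal residual graft when the addition of amnion is what is being tested, and section 13.1 itself compares residual graft across groups. The CBCT sentence there still carries an undefined label and a natural-fill quantity with no source.

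**Conclusion.** The point holds in a conditional form. As written, CBCT fill is graft plus bone to an unknown degree, and neither its week-7 difference between arms nor its change from the graft-filled baseline can be read as new bone without further assumptions. The error is the visibility of the graft times the between-arm difference in residual graft. It is zero if either factor is zero. In the illustrations it reaches 25 points, enough to turn a 10-point gain into an apparent 15-point loss. Those percentages are assumed, and the documents settle neither factor.

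Total radiographic fill at week 7 is valid under that name, and the post-graft scan is a usable baseline for ridge dimensions (Aim 2). The plan should be amended, because the change costs almost nothing and settles in advance which measure supports a new-bone claim.

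**What to change.** 1. **Section 13.1:** label the CBCT reading 'radiographic fill (graft plus bone)', define how it is measured (region, threshold, reader blinding), delete natural bone fill, and state that the reading will not be interpreted as new bone.
2. **Sections 2.3 and 13.1:** state that claims of new bone formation (the new-bone content of Aim 4 and Hypothesis-2) rest on histomorphometric % new bone at week 8, reported with % residual graft.
3. **Section 13.4:** name the measurement behind bone growth, and do not use the CBCT change from the graft-filled baseline for it.
4. Keep week-7 radiographic fill at all sites as a supporting outcome, alongside ridge height and width.
5. **Section 5.0:** reconcile the two descriptions of the first scan.
6. Report by arm the number of participants without a core, and why.

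The cost is wording only, since both scans and the biopsy are already scheduled. The downside is that new bone is judged on one site per participant, so only large differences are detectable, and missing cores at poorly healed sites could bias the comparison. Items 4 and 6 make that loss visible but do not remove it.
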